## **5.9 Receiving, Storage, Dispensing and Return**

### **5.9.1 Receipt of Drug Supplies**

Upon receipt of the drug supplies from the manufacturers, an inventory will be performed by the IDS and a drug receipt log filled out and signed by the IDS staff person accepting the shipment. The designated study staff will count and verify that the shipment contains all the items noted in the shipment inventory. Any damaged or unusable study drug in a given shipment will be documented in the study files.

### **5.9.2 Storage**

TRH will be stored in IDS at -20 degrees Celsius or cooler. LT4 and LT3 will be stored in a dry place and protected from light at room temperature.

### **5.9.3 Dispensing of Study Drug**

TRH obtained from the IDS pharmacy will be given to patients as an injection in the CTRC. LT4 and LT3 obtained from the IDS pharmacy will be given to patients as oral capsules to take home. Regular study drug reconciliation will be performed to document drug assigned, drug consumed, and drug remaining. This reconciliation will be logged on the drug reconciliation form, and signed and dated by the study team.

### **5.9.4 Return or Destruction of Study Drug**

All study participants will return unused capsules of study drug to study staff at Visits 2 and 3, which will be given to IDS. At the completion of the study, there will be a final reconciliation of drug shipped, drug consumed, and drug remaining. This reconciliation will be logged on the drug reconciliation form, signed and dated. Any discrepancies noted will be investigated, resolved, and documented prior to return or destruction of unused study drug. Drug destroyed on site will be documented in the study files.

## **6 Study Procedures**

### **6.1 Screening Visit (Day -60 to Day -1)**

Upon arrival at the CTRC, the participant will review and sign the IRB-approved consent form. The participant will also review an optional exploratory genetics research study IRB-approved consent form and sign only if they agree to participate in the optional study. They will then be assigned a unique screening visit identification number. Participants will be asked for a thorough history detailing their past medical history, current medications, and social habits. They will perform the MMSE. The research nurse will measure weight, height, blood pressure, heart rate, and perform a 12 lead ECG. A study investigator will perform a physical examination. Subjects will have blood drawn to evaluate lab parameters for eligibility criteria. A free thyroxine (FT4) level in conjunction with a TSH level will be sent to confirm subclinical hypothyroidism. The thyroid stimulating hormone (TSH) test obtained during the screening visit is measured at least 4 weeks after the last elevated TSH. Instructions for use of the activity and heart rate monitors will be given to each participant. Participants will then be discharged to home. If participants are eligible for the study, an activity and heart rate monitor will be mailed to their home. Participants will be advised to wear the activity and heart rate monitor for 4 days) prior to the first study

CONFIDENTIAL

This material is the property of the University of Pennsylvania. Do not disclose or use except as authorized in writing by the study sponsor

visit. The heart rate band will be moistened with either water or gel per the activity monitor instructions. Participants will also be given a log to record when they place their heart rate and activity monitors on and off.

## **6.2 Visit 1 (Day 1)**

Participants will arrive at 7:30 am after a 12-hour fast. Weight and vital signs including heart rate, rectal temperature, and blood pressure will be measured. The activity and heart rate monitors will be collected. An REE evaluation by indirect calorimetry will be completed.

An IV will be inserted into the forearm and blood will be collected at times -5 and 0, followed by injection of 200 µg TRH.[28] Additional blood will be collected at 5, 10, 15, 20, 30, 60, 120, and 180 minutes, immediately processed, and stored at -80 degrees for measures of TSH, free T4, and total T3 (all time points), prolactin, alpha subunit, reverse T3 (0, 60, and 180 minutes), and a lipid profile (time 0). Additional samples at the 0, 120, and 180 time points will be processed and saved for TSH bioactivity measurements and TSH structure evaluation. If the participant consents to the optional exploratory genetic research study, then a sample will be collected, processed and saved for genetic testing at one study visit only (time -5).

Blood pressure will be monitored before administration of TRH, and at 5, 15, 30, 60, 120, 180 minutes.

Questions about health status, quality of life, and hypothyroid symptoms will be completed. Digit symbol substitution test will be completed.

Participants will be provided with lunch and undergo a DXA scan.

Participants will then undergo arterial tonometry and Doppler echocardiography testing. Assessment of arterial load will be made from this data.

Arterial tonometry: We will use a commercially available system (SphygmoCor, AtCor Medical) that uses a high-fidelity applanation tonometer (Millar Instruments; Houston, TX). The tonometer will be used to record carotid, radial and femoral arterial pressure waveforms. Mean brachial pressure will be obtained from a radial waveform calibrated with brachial systolic and diastolic pressures, measured with a validated oscillometric device. Diastolic and mean pressures will then be used to calibrate the carotid pressure waveform. Carotid-femoral and carotid-radial pulse wave velocity (PWV) will be computed from the time delay between the waveform foot on these arterial sites and the distance between the sites (measured on the body surface), where PWV = distance/time.

Doppler echocardiography: will be performed using a standard protocol, which will include parasternal views and apical views of the left ventricle. It will also include pulsed-wave Doppler interrogation of flow velocities in the LV outflow tract, mitral inflow and mitral annular velocities. Flow volume will be computed by multiplying LV outflow tract flow velocity by the LV outflow tract cross-sectional area measured with 3D echocardiography.

CONFIDENTIAL

This material is the property of the University of Pennsylvania. Do not disclose or use except as authorized in writing by the study sponsor

Diastolic function will be assessed using standard parameters from mitral inflow and mitral annular tissue velocity profiles.

Assessment of arterial load will be performed via pressure-flow analyses and will include assessments of proximal aortic characteristic impedance, total arterial compliance, and reflection magnitude computed using linear wave separation analysis, using central pressure and flow waveforms measured via arterial tonometry and Doppler echocardiography, respectively.

Arterial tonometry is non-invasive and does not have any known risks.

During various procedures (arterial tonometry, echocardiography), we will use adhesive electrodes attached to the participant's skin to record the electrical signal from the heart. These may occasionally cause skin itching and irritation.

Arterial tonometry and Doppler echocardiographic examinations will only be performed by appropriately trained personnel as per our institutional standards.

Prior to the end of the visit the participant will receive verbal and written instructions on thyroid hormone dosing and provided with sufficient study medication for 6 weeks. Then they will be discharged home.

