### **1.5 Dose Rationale and Risk/Benefits**

#### **TRH stimulation testing:**

TRH has a short half-life and does not exhibit a sustained biological effect after a single intravenous bolus. For decades, TRH has been intravenously administered to a variety of study populations, including patients with thyroid, pituitary, and hypothalamic disorders.[10, 11, 25] In this study we will be using the standard clinical dose of 200 µg at three time points. This dose has been used in studies of dynamic pituitary testing utilizing TRH stimulation testing.[25, 26] Side effects have been reported in about 50% of patients, but side effects are generally minor and persist for only a few minutes following injection.

These side effects include[27]:

Most frequent: transient nausea, flushing, palpitations (without change in heart rate), lightheadedness, bad taste in mouth, abdominal discomfort, dry mouth, and an urge to urinate

Less frequent: anxiety, sweating, tightness in throat (without change in oxygenation or respiration), pressure in chest, tingling sensation, and drowsiness

Uncommon: change in blood pressure, seizure

The mean elevation of blood pressure reported was 16 mm of mercury. The peak blood pressure elevation occurred between one and five minutes, with a return to baseline blood pressure levels within ten minutes.[11] Participants with uncontrolled blood pressure or history of ischemic cardiac disease or stroke will be excluded.

Seizures have only been reported in those with a history of seizure disorder. Individuals with a history of seizure will be excluded.

No direct benefits are expected to result from TRH administration.

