### 5.4 Preparation and Administration of Study Drug

TRH in powder form must be stored at -20 degrees Celsius or cooler. LT4 and LT3 must be stored at room temperature. Storage, preparation, labeling and dispensing of all study drugs (TRH, LT4, and LT3) will be done by the IDS (available at [contact] or, for after-hours emergencies, [contact]) in accordance with HUP's Pharmacy Policy and

CONFIDENTIAL

This material is the property of the University of Pennsylvania. Do not disclose or use except as authorized in writing by the study sponsor

Procedures. Each drug label will include the subject's unique identification number, date dispensed, and directions for use.

One prefilled syringe containing 200 µg TRH will be administered to participants by a CTRC nurse in the CTRC at each study visit.

TRH should be administered with the patient in the supine position. It will be administered as an intravenous bolus over 1 minute. The patient should remain supine until all of the post-injection blood draws have been completed. The patient should urinate prior to the procedure as they may feel an urge to urinate after the TRH is administered.

The LT4 and LT3 will be packaged in identical coded dose-tailored capsules containing either LT4 or LT3. The participants will be given sufficient study medication for 6 weeks at the start of each treatment regimen (LT4 or LT3). Participants will obtain TSH level checks at 4-week intervals, after which they will be provided with additional study medication as needed. If a dose change is required, new study medication will be mailed overnight to participants within 5 days of review of the lab results. Unused capsules will be returned to IDS at Visits 2 and 3.

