### **6.5 Visit 2**

Participants will repeat all measures from Visit 1 at this study visit on their first thyroid preparation (LT4 or LT3). Subjects will stop taking study drug for 4 weeks after the study visit 2. During this wash-out period once every two weeks a phone contact will continue to be made by one of the study team members to inquire if the participant has experienced any adverse events. Specifically, the participant will be asked if they have any symptoms

CONFIDENTIAL

This material is the property of the University of Pennsylvania. Do not disclose or use except as authorized in writing by the study sponsor

of palpitations or shortness of breath. A six week supply of crossover study drug will either be sent home with the participant from study visit 2 or it will be mailed to them. Subjects will be instructed to begin this study drug 4 weeks after study visit 2. TSH level will be checked 4 weeks after starting the new study drug, and all study procedures for medication titration and TSH checks will be repeated as above.

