### **Adverse Event**

An **adverse event** (AE) is any symptom, sign, illness or experience that develops or worsens in severity during the course of the study. Intercurrent illnesses or injuries should be regarded as adverse events. Abnormal results of diagnostic procedures are considered to be adverse events if the abnormality:

- results in study withdrawal
- is associated with a serious adverse event
- is associated with clinical signs or symptoms
- leads to additional treatment or to further diagnostic tests
- is considered by the investigator to be of clinical significance

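### Section 6.2 takes only one blood pressure reading, at 5 minutes, in the 10 minutes in which section 1.5 places the TRH pressure rise and recovery; a reading at 2–3 minutes would fit better (minor, safety monitoring only)

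*Combined protocol and SAP*

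**What the plan says.** Section 1.5 (TRH stimulation testing) reports a mean pressure rise of 16 mm Hg after TRH and gives its time course: "The peak blood pressure elevation occurred between one and five minutes, with a return to baseline blood pressure levels within ten minutes". The same section ranks the effect among the rarer ones: "Uncommon: change in blood pressure, seizure".

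Section 6.2 sets the readings for Visit 1: "Blood pressure will be monitored before administration of TRH, and at 5, 15, 30, 60, 120, 180 minutes". It samples blood more densely over the same period: "Additional blood will be collected at 5, 10, 15, 20, 30, 60, 120, and 180 minutes". Two draws come before the drug ("blood will be collected at times -5 and 0, followed by injection of" TRH), so the time-0 draw precedes the injection. On the injection itself, section 5.4 says: "It will be administered as an intravenous bolus over 1 minute".

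Section 6.5 carries the schedule forward ("Participants will repeat all measures from Visit 1 at this study visit"), and section 6.6 repeats Visit 2 at Visit 3. No other section schedules a pressure reading in the first 10 minutes after TRH.

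**The concern.** The protocol names a pressure rise as a TRH risk and states when it happens, but most of the readings are placed where it expects nothing to be happening. An early peak that is already falling at 5 minutes is recorded as smaller than it was.

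What is at stake is the safety record, not the efficacy analysis. Participants are 70 or older, and section 4.2 excludes uncontrolled hypertension only above 160/100. A short rise without symptoms would not come up in questioning or in the next-day call of section 6.7, so the cuff is the only scheduled way of seeing its size.

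**Working it through.** **1. Count of readings against the stated time course (no model needed).** Inputs are the post-dose readings in section 6.2 (5, 15, 30, 60, 120, 180 minutes) and the two windows in section 1.5 (peak at 1–5 minutes, recovery by 10).

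| | Present schedule | With 2–3 min added | With 2–3 and 10 min added |
|---|---|---|---|
| Readings in 0–10 min | 1 (5) | 2 (2–3, 5) | 3 (2–3, 5, 10) |
| Readings in 1–5 min | 1 (5, on the edge) | 2 | 2 |
| Strictly inside 1–5 min | 0 | 1 | 1 |
| Earliest reading that can show failed recovery | 15 min | 15 min | 10 min |

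At present five of six post-dose readings come after the stated recovery. This count is the finding.

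**2. How much of a peak might be missed (illustrative only).** The documents give no curve. Assume a peak of 16 mm Hg at time p between 1 and 5 minutes, and a linear rise from time 0. For the decay, assume one of two shapes:

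- linear to zero at 10 minutes: value at t = 16 × (10 − t)/(10 − p)
- exponential to 5% of peak at 10 minutes: value at t = 16 × 0.05^((t − p)/(10 − p))

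At t = 5:

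| Peak time p (min) | 1 | 2 | 3 | 4 | 5 |
|---|---|---|---|---|---|
| Linear, mm Hg | 8.9 | 10.0 | 11.4 | 13.3 | 16.0 |
| Linear, % of peak | 56 | 62 | 71 | 83 | 100 |
| Exponential, mm Hg | 4.2 | 5.2 | 6.8 | 9.7 | 16.0 |
| Exponential, % of peak | 26 | 33 | 42 | 61 | 100 |

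If the rise is instead held across 1–5 minutes, the 5-minute reading shows about 100%.

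**3. Average capture, and the effect of the added reading.** Assume also that peak times are spread evenly over 1–5 minutes. For linear decay the mean capture at 5 minutes is (1/4) × ∫ 5/(10 − p) dp from 1 to 5 = (5/4) × ln(9/5) = 73%. The exponential case, done numerically, gives 49%. Taking the larger of the readings at s and at 5 minutes, with s between 2 and 3, gives:

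| | 5 min only | s and 5 min |
|---|---|---|
| Mean, linear | 73% | 86–89% |
| Mean, exponential | 49% | 76–78% |
| Worst case, linear | 56% | 70% (s = 2), 75% (s = 2.5), 78% (s = 3) |
| Worst case, exponential | 26% | 54% (s = 2), 61% (s = 2.5), 51% (s = 3) |

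The 10-minute reading adds nothing to these figures.

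**4. Sensitivity to time zero.** Section 1.5 does not say whether its minutes run from the start or the end of the injection, which lasts 1 minute. If they run from the end and section 6.2's from the start, the 5-minute reading falls at 4 minutes on section 1.5's clock. For linear decay the mean is then (1/4) × [6 × ln(9/6) + 4 × ln(5/4)] = 83%, and for exponential decay it is 67%. Under the opposite mismatch the reading falls at 6 minutes, and the means are ln(9/5) = 59% and, for exponential, 30%. One minute of ambiguity in the clock therefore moves the average about as much as the added reading does in the linear case.

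**The case against.** The strongest reply is that nothing here is an error. The 5-minute reading lies inside the stated peak window, and no section promises to capture the maximum. A nurse gives the injection, staff draw blood at 5 and 10 minutes, and section 8.2 asks for examination as appropriate at each contact, so an unscheduled reading is not barred. The exclusions and the supine posture already limit risk. All of this stands, and it keeps the point minor.

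Three stronger readings might be inferred, and the documents do not support them.

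- *The schedule misses the pressure rise or contradicts section 1.5.* It does not. One reading falls in the peak window, and up to 30 × 3 = 90 five-minute readings will show some of the rise.
- *Adverse events will be under-recorded.* Section 8.1 does say that an adverse event "is any symptom, sign, illness or experience that develops or worsens in severity during the course of the study". It then limits abnormal diagnostic results to those that lead to withdrawal, accompany a serious event or symptoms, prompt treatment or further tests, or are judged clinically significant. Whether a cuff value is a sign or a diagnostic result is arguable, but a brief symptomless rise of the kind section 1.5 already describes need not count.
- *Recovery goes unchecked.* The 15-minute reading would show a failure to recover. A 10-minute reading brings that knowledge forward by 5 minutes, and no action in the plan depends on it.

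The objection that the percentages are nearly all assumption is also right. In addition, section 1.5 credits the time course to a cited study that section 1.2 describes as giving 100–800 µg to 79 healthy men. This trial gives 200 µg to men and women of 70 and over, so the 16 mm Hg mean may not carry across in either direction.

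**Conclusion.** The point holds as a minor mismatch between the protocol's own time course and its cuff schedule: one of six post-dose readings falls in the 10 minutes that matter, at the edge of the peak range, at all three visits. The consequence is limited to possible understatement of an early, short-lived peak. The primary analysis is untouched, and no endpoint, threshold or stopping rule uses these readings.

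The count rests on the documents alone. The share of the peak that is lost does not. It runs from 0 to 74% (100 − 26) across the illustrative shapes, and depends on the curve, the clock and a mean borrowed from another population. A reader should not take from it that a material safety signal is being missed. It shows only that the present timing can understate an early peak, and that one better-placed reading reduces this without removing it.

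**What to change.** In section 6.2, applying to Visits 1–3, keep every existing reading and add one at 2–3 minutes. Suggested text: *Blood pressure is taken before TRH and then at 2–3, 5, 15, 30, 60, 120 and 180 minutes, timed from the start of the 1-minute injection, using the arm without the IV.* Stating the zero point also settles section 6.2's clock and agrees with its time-0 draw, which comes just before the injection.

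Optionally, add a reading at 10 minutes, taken with the blood draw already scheduled then, if an earlier check of recovery is wanted.

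The cost is one sentence and 3 more readings per participant (at most 3 × 30 = 90), or 6 per participant (at most 180) with the optional reading. Staff are already with the participant. The downside is one or two more cuff inflations per visit close to blood draws, which using the arm without the IV eases.

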**Secondary Objectives:**

[figure not shown]
To assess changes in between baseline and each thyroid preparation in:

- 1) unstimulated TSH bioactivity
- 2) resting energy expenditure (REE)
- 3) body temperature
- 4) weight
- 5) body composition
- 6) lipids
- 7) bone density
- 8) heart rate
- 9) physical activity
- 10) hypothyroid and hyperthyroid symptoms
- 11) health status and well-being assessment with SF-36
- 12) cognitive testing with digit symbol substitution test
- 13) arterial tonometry, doppler echocardiography, and arterial load assessment

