### **3.3 Secondary Study Endpoints**

The following endpoints will be measured at each study visit:

1. Unstimulated TSH bioactivity
2. Resting energy expenditure (REE) evaluation by indirect calorimetry
3. Weight
4. Body composition including body fat (percent and total), free fat mass, and bone density measured by dual energy x-ray absorptiometry (DXA)
5. Lipid profile via laboratory measurements
6. SF-36 for health status, hypothyroid symptoms (Appendix 2)
7. Heart rate and physical activity via actigraphy
8. Digit symbol substitution test
9. Body temperature using rectal temperature measurement
10. Optional exploratory genetic testing (one study visit only)
11. arterial tonometry, Doppler echocardiography, and arterial load assessment

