## **6.6 Visit 3**

Participants will repeat all measures from Visit 2 at this final study visit on their second thyroid preparation (LT4 or LT3). The study will be complete.

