### 7.2 Statistical Methods

All statistical analyses will be performed under consultation with [name], Ph.D., a CTRC biostatistician. Our primary goal will be to assess changes in TRH stimulation test parameters at baseline compared to each thyroid hormone supplementation (LT4 or LT3) and our secondary goal will be to compare physiologic responses to LT4 and LT3 therapy from baseline. The area under the curve (AUC) for TRH-stimulated TSH response will be calculated using the trapezoidal rule. The maximum serum TSH concentration following TRH administration ( $TSH_{max}$ ) will be obtained by direct inspection of the serum concentration-time profiles. Changes in TSH bioactivity, free T4, and total T3 will be determined using the higher of the 120 or 180 minute post-TRH values. Paired t-tests will be used to examine change from baseline for each preparation, and two-tailed tests will be used to compare data between treatment arms. Nonparametric tests will be employed as needed. The primary outcomes will be the changes in TRH stimulation test parameters (AUC,  $TSH_{max}$ ,  $\Delta$  TSH bioactivity,  $\Delta$  free T4,  $\Delta$  total T3). Additional outcomes will include changes in unstimulated TSH bioactivity, REE, body temperature, weight, body composition, lipids, physical actigraphy and heart rate, cognitive testing, symptoms, arterial tonometry, and Doppler echocardiography.

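### Change from baseline on the digit symbol substitution test mixes practice gain with drug effect, because the off-drug attempt always comes first

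*Combined protocol and SAP*

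**What the plan says.** The combined protocol and SAP fixes the order of testing as follows.

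- **Screening (6.1).** The only cognitive test listed is the MMSE: "They will perform the MMSE".
- **Visit 1 (6.2).** "Digit symbol substitution test will be completed". Section 3.1 starts the capsules the next morning, so this attempt is off drug.
- **Visit 2 (6.5).** "Participants will repeat all measures from Visit 1 at this study visit on their first thyroid preparation (LT4 or LT3".
- **Visit 3 (6.6).** "Participants will repeat all measures from Visit 2 at this final study visit on their second thyroid preparation (LT4 or LT3".

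Section 2 lists "cognitive testing with digit symbol substitution test" as item 12 of 13 secondary objectives, all framed as changes between baseline and each preparation. Section 3.3 repeats it as secondary endpoint 8. Section 7.2 states that "our secondary goal will be to compare physiologic responses to LT4 and LT3 therapy from baseline". More directly for this point, it counts cognition among the additional change outcomes ("lipids, physical actigraphy and heart rate, cognitive testing, symptoms, arterial tonometry, and Doppler echocardiography"), prescribes a paired t-test against baseline for each preparation, and adds a two-tailed comparison between the treatment arms.

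Section 5.3 randomises only the order of LT4 and LT3. Sections 5.2 and 6.5 give the 4-week wash-out phone contacts but no test visit.

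**The concern.** The digit symbol substitution test is a performance task, and repeating it can itself raise the score. Within this study, the off-drug score is always attempt 1 and the on-drug scores are always attempts 2 and 3. Attempt number and treatment are therefore confounded in each from-baseline contrast. The documents mention no practice run, alternate test form, untreated retest, or adjustment for practice or period.

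A practice gain would appear as improvement on LT4 and again on LT3. The two results could look like independent replication, although both are measured against the same first attempt. Section 1.1 says it is unclear whether people with subclinical hypothyroidism gain from thyroid hormone, so an apparent cognitive improvement in people aged 70 and over could be taken as evidence on that question.

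**Working it through.** **1. The plan's own figure.** Section 7.1 gives 30 enrolled, 15% dropout, alpha 0.05, 80% power and a detectable change of 0.58 SD.

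- Completers: 30 × 0.85 = 25.5.
- Method: paired t-test, two-sided 5%, n − 1 degrees of freedom, noncentrality d√n.
- Detectable d at 80% power: 0.584 (n = 25), 0.578 (n = 25.5), 0.572 (n = 26).

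The 0.58 reproduces, so the same test and n = 25 are used below.

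**2. Effect of a practice gain on one drug's test.** Let g be the practice gain in SDs of the change score, with no drug effect. The paired t statistic then has noncentrality g√25 = 5g, and the null is rejected when |t| exceeds the 97.5% point of t with 24 degrees of freedom. The documents give no value for g; the values below are assumptions.

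| Assumed g | 5g | Chance of a significant result |
|---|---|---|
| 0 | 0 | 5.0% |
| 0.1 | 0.5 | 7.7% |
| 0.2 | 1.0 | 16.1% |
| 0.3 | 1.5 | 30.2% |
| 0.4 | 2.0 | 48.4% |
| 0.5 | 2.5 | 67.0% |

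With n = 26 the figures barely move (7.8% at g = 0.1, 68.8% at g = 0.5).

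**3. Both drugs together.** A simulation used 13 completers per sequence, independent visit errors, SD of change 1, and a gain of 0.3 at both later visits. Mean change shifted by +0.30 on each drug. Each drug showed significant improvement in about 31% of trials, at least one did in 46%, and both did in 16%. Independent tests would give both in about 0.31 × 0.31 = 10%; the excess comes from the shared baseline.

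**4. The LT4-LT3 comparison.** Let the gain be g2 at Visit 2 and g3 at Visit 3, with n1 completers taking LT4 first and n2 taking LT3 first.

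- Bias in LT4 minus baseline: (n1·g2 + n2·g3)/(n1 + n2). For LT3, swap n1 and n2. With equal sequences both equal (g2 + g3)/2; for gains of 0.4 and 0.6 that is 0.50.
- Bias in LT4 minus LT3: (g3 − g2)(n2 − n1)/(n1 + n2). With equal sequences this is 0. With 15 and 10 completers and gains of 0.4 and 0.6 it is 0.2 × (−5/25) = −0.04 SD.

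In simulation the two-sided error of the between-drug test stayed near 5% in both cases. The gain common to both on-drug visits cancels between drugs. Any further gain from Visit 2 to Visit 3 is a period effect, which a period term removes.

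**The case against.** **The size is assumed.** The documents give no practice gain, SD of change or retest reliability for this test. The assumed range runs from nearly harmless (8%) to serious (67%), and nothing places this trial within it. Retesting is not immediate: the first TSH check comes after 4 weeks on drug, Visit 2 may fall up to four weeks after the last TSH (6.4), Visit 3 follows a 4-week wash-out and a second titration, and total follow-up is 14 to 78 weeks (4.4.1). The gain may well be small. This stands, and the percentages are illustrative only. It does not remove the confounding, because no trial data can estimate the gain separately from a drug effect common to both preparations.

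**The outcome is minor.** It is one secondary objective of 13, and every from-baseline contrast here lacks an untreated control. This also stands. The test differs from most of the other outcomes in that taking it can itself change the score.

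**The clean comparison is already planned.** Section 7.2 provides a between-arm comparison, and the drugs are blinded. True, but nothing in the plan makes it the basis for a cognitive conclusion, and no period term is named.

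**Stronger readings.** A reader might infer that a practice gain will be reported as a cognitive effect of both drugs. No section commits to that reading: the title calls the study mechanistic, and sections 1.5 and 5.2 expect no direct benefit from LT4 or LT3. A reader might also infer that Visit 1 is each participant's first ever exposure to the test. It is the first in this study; earlier testing is not addressed.

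**Conclusion.** The point holds as a limit on interpretation. The planned paired change from baseline on this test cannot separate practice from drug effect for either preparation, and randomising the drug order cannot repair that. An improvement on both drugs could be misread as cognitive benefit.

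The size is unknown. The 8% to 67% range rests on an assumed gain of 0.1 to 0.5 SD of the change score, 25 completers, no drug effect and a two-sided 5% test. The joint figures also assume independent visit errors.

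Two wider inferences are not supported. The LT4-LT3 comparison is not materially affected: in the unequal-sequence example its bias was 0.04 SD, with error near 5%. The primary TRH-test endpoints and the sample size do not depend on this test at all.

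**What to change.** - **Section 7.2.** Base any conclusion about cognition on the blinded within-person LT4-LT3 comparison, with a period term. Report the from-baseline change on this test as descriptive and uncontrolled for practice.
- **Section 2, secondary objective 12.** Note the same limit. The objective asks about change from baseline, and the LT4-LT3 comparison does not answer that question.
- **Section 6.1.** For participants not yet screened, add one brief unscored practice administration next to the MMSE.

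The wording changes cost almost nothing and alter no visit, sample size or primary analysis. The practice run should add a few minutes at screening (an estimate; the documents give no administration time). It is only a partial remedy, because screening can fall up to 60 days before Visit 1 and one run may not remove the learning effect. The descriptive label is therefore needed with or without it.
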